8.1. Safety Assessments

Planned time points for all safety assessments are provided in the SoA.

8.1.1. Physical Examinations

- A complete physical examination will include, at a minimum, assessments of the general
 appearance, head, ears, eyes, nose, throat, neck, skin, cardiovascular system, respiratory
 system, abdominal system and nervous system.
- Investigators should pay special attention to clinical signs related to previous serious illnesses.

8.1.2. Vital Signs

- Vital signs (to be taken before blood collection for laboratory tests).
- Blood pressure and pulse measurements will be assessed in the supine with a completely automated device. Manual techniques will be used only if an automated device is not available.
- Blood pressure and pulse measurements should be preceded by at least 5 minutes of rest for the participant in a quiet setting without distractions (e.g., television, cell phones).

8.1.3. Electrocardiograms

- 12-lead ECG will be obtained as outlined in the SoA (see Section 1.3).
- ECGs will be reviewed locally, for safety findings, which should be documented by the Investigator. Paper ECGs will remain at site (as source documents).
- Results are to be documented in the eCRF as normal, or abnormal and whether clinically significant.

8.1.4. Clinical Safety Laboratory Assessments

- See Appendix 2 for the list of clinical laboratory tests to be performed and to the SoA for the timing and frequency.
- The investigator must review the laboratory report, document this review, and record any clinically relevant changes occurring during the study in the AE section of the CRF. The laboratory reports must be filed with the source documents. Clinically significant abnormal laboratory findings are those which are not associated with the underlying disease, unless judged by the investigator to be more severe than expected for the participant's condition.
- All laboratory tests with values considered clinically significantly abnormal during participation in the study or within two (2) weeks after the last dose of study intervention should be repeated until the values return to normal or baseline or are no longer considered clinically significant by the investigator or medical monitor.
 - If such values do not return to normal/baseline within a period of time judged reasonable by the investigator, the etiology should be identified, and the sponsor notified.
 - o All protocol-required laboratory assessments, as defined in Appendix 2, must be conducted in accordance with the laboratory manual and the SoA.

 If laboratory values from non-protocol specified laboratory assessments performed at the institution's local laboratory require a change in participant management or are considered clinically significant by the investigator (e.g., SAE or AE or dose modification), then the results must be recorded in the CRF.

8.1.5. Suicidal Risk Monitoring

Not done.

8.2. Efficacy Assessments

Goniometric measurement of "lateral" and "anterior" displacement is determined using a wall goniometer and expressing the value in degrees.

Site personnel who are to be involved in performing the efficacy assessments, UMSARS, the MSA-QoL, the MoCA, the UDRS must be experienced in the use of the various scales and questionnaires.

To ensure consistency of ratings on each efficacy measure for each participant during the study, the same rater should perform the assessments where possible.

Wherever possible the MSA QoL should be completed by the participant. However, in the case of the participant's incapacity, the participant's caregiver may help complete it based on information reported by the participant.

8.3. Adverse Events and Serious Adverse Events

The definitions of an AE or SAE can be found in Appendix 3.

AE will be reported by the participant (or, when appropriate, by a caregiver, surrogate, or the participant's legally authorized representative).

The investigator and any qualified designees are responsible for detecting, documenting, and recording events that meet the definition of an AE or SAE and remain responsible for following up AEs that are serious, considered related to the study intervention or study procedures, or that caused the participant to discontinue the study (see Section 7)

8.3.1. Time Period and Frequency for Collecting AE and SAE Information

All (S)AEs will be collected from the signing of the informed consent form (ICF) until the follow-up visit at the time points specified in the SoA (Section 1.3).

Medical occurrences that begin before the start of study intervention but after obtaining informed consent will be recorded on the Medical History/Current Medical Conditions section of the case report form (CRF) not the AE section.

All SAEs will be recorded and reported to the sponsor or designee within 24 hours, as indicated in Appendix 3. The investigator will submit any updated SAE data to the sponsor within 24 hours of it being available.

Investigators are not obligated to actively seek AE or SAE after conclusion of the study participation. However, if the investigator learns of any SAE, including a death, at any time after a participant has been discharged from the study, and he/she considers the event to be reasonably related to the study intervention or study participation, the investigator must promptly notify the sponsor.

The method of recording, evaluating, and assessing causality of AE and SAE and the procedures for completing and transmitting SAE reports are provided in Appendix 3.

8.3.2. Method of Detecting AEs and SAEs

Care will be taken not to introduce bias when detecting AEs and/or SAEs. Open-ended and non-leading verbal questioning of the participant is the preferred method to inquire about AE occurrences.

8.3.3. Follow-up of AEs and SAEs

After the initial AE/SAE report, the investigator is required to proactively follow each participant at subsequent visits/contacts. All (S)AEs, will be followed until resolution, stabilization, the event is otherwise explained, or the participant is lost to follow-up (as defined in Section 7.3). Further information on follow-up procedures is given in Appendix 3.

8.3.4. Regulatory Reporting Requirements for SAEs

- Prompt notification by the investigator to the sponsor of a SAE is essential so that legal obligations and ethical responsibilities towards the safety of participants and the safety of a study intervention under clinical investigation are met.
- The sponsor has a legal responsibility to notify both the local regulatory authority and other regulatory agencies about the safety of a study intervention under clinical investigation. The sponsor will comply with country-specific regulatory requirements relating to safety reporting to the regulatory authority, Institutional Review Boards (IRB)/Independent Ethics Committees (IEC), and investigators.
- Investigator safety reports must be prepared for suspected unexpected serious adverse reactions (SUSAR) according to local regulatory requirements and sponsor policy and forwarded to investigators as necessary.
- An investigator who receives an investigator safety report describing a SAE or other specific safety information (eg, summary or listing of SAEs) from the sponsor will review and then file it along with the Investigator's Brochure and will notify the IRB/IEC, if appropriate according to local requirements.

8.3.5. Pregnancy

• Details of all pregnancies in female will be collected after the start of study intervention and until 1 month after the last dose of study drug

- If a pregnancy is reported, the investigator should inform the sponsor within 24 hours of learning of the pregnancy and should follow the procedures outlined in Appendix 4.
- Abnormal pregnancy outcomes (e.g., spontaneous abortion, fetal death, stillbirth, congenital anomalies, ectopic pregnancy) are considered SAEs.

8.3.6. Disease-Related Events and/or Disease-Related Outcomes Not Qualifying as AEs or SAEs

Not applicable

8.4. Treatment of Overdose

The anticipated pattern of events or symptoms following intentional or accidental overdose with safinamide is that related to its pharmacodynamic profile (MAO-B inhibition with activity dependent inhibition of sodium channels). The symptoms of excessive MAO-B inhibition (increase in dopamine level) could include hypertension, postural hypotension, hallucinations, agitation, nausea, vomiting and dyskinesia.

There is no known antidote to safinamide or any specific treatment for a safinamide overdose. If a significant overdose should occur, safinamide treatment should be discontinued and supportive treatment should be administered as clinically indicated.

In the event of an overdose, the Investigator should:

- Contact the Medical Monitor immediately.
- Closely monitor the participant for any AE/SAE or laboratory abnormalities
- Obtain a plasma sample for PK analysis if requested by the Medical Monitor (determined on a case-by-case basis).
- Document the quantity of the excess dose as well as the duration of the overdose in the CRF

Decisions regarding dose interruptions or modifications will be made by the investigator in consultation with the Medical Monitor based on the clinical evaluation of the participant.

8.5. Pharmacokinetics

PK parameters are not evaluated in this study.

8.6. Pharmacodynamics

Pharmacodynamic parameters are not evaluated in this study.

8.7. Genetics

Genetics are not evaluated in this study.

8.8. Biomarkers

Biomarkers are not evaluated in this study.

8.9. Health Economics

Not applicable

9. Statistical Considerations

9.1. Statistical Hypotheses

Safety data will be presented descriptively, thus no formal hypothesis for safety will be tested. Efficacy endpoints will be tested with hypothesis of the form:

H0: $\mu_{Test} = \mu_{Placebo}$

H1: $\mu_{Test} \neq \mu_{Placebo}$ for continuous variables

H0: $\pi_{\text{Test}} = \pi_{\text{Placebo}}$

H1: $\pi_{Test} \neq \pi_{Placebo}$ for categorical variables

where μ is the mean in the population and π is the proportion in the population

9.2. Sample Size Determination

As this is a pilot study, no formal sample size has been calculated.

The sample size was selected based on previous studies in this population and the safety profile of salfinamide in the marketed indication of Parkinson's Disease. The current study enrolls 26 active vs 14 placebo. While there are few recent efficacy studies of symptomatic therapy in MSA, there is a more recent study of the efficacy of rasagiline (Poewe, W., et al. (2015) that randomized 84 subjects to rasagiline and 90 to placebo. While this study failed to find a therapeutic effect of rasagiline, it demonstrated that this sample size would have been adequate to detect a clinically relevant change in symptoms. A study of that size was deemed too large as an initial safety study.

Previous studies of salfinamide in Parkinson's Disease showed Adverse Event rates in treated groups to be less than 10% in excess of placebo (Borgohain, R, et al. 2014). In that occasion, it was deemed reasonable to perform a trial with approximately 56 participants - randomized at a 2:1 ratio active: placebo - to achieve 48 randomly assigned to study intervention and 40 evaluable participants for an estimated total of respectively 26 and 14 evaluable participants per intervention group - and it was judged to be sufficient to provide an estimate as to whether AEs are likely to be within this range in the MSA patient population at this dose.

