4.1. Overall Design

The overall design is a parallel group, placebo controlled, double blind study.

The target population are participants diagnosed, less than two years ago, with possible or probable parkinsonian variant of Multiple System Atrophy (Gilman, 2008) who are on stable doses of levodopa and/or dopamine agonist, anticholinergic and/or amantadine.

Trial participation will be up to a maximum duration of 14 weeks and will comprise a screening period (up to 2 weeks), a run in period of 2 weeks (week 1 – week 2) during which study participants will receive 1 tablet (either 100 mg safinamide or matching placebo) followed by a treatment period (week3 – week 12), during which they will receive two tablets (200 mg safinamide or matching placebo) once daily, taken in the morning in addition to their daily levodopa dose (and/or the above mentioned allowed MSA treatments). In the event the study participant does not tolerate 2 tablets, they can drop down to 1 tablet per day and remain in the study at that dose level.

A telephone follow-up call will be performed 2 weeks after the end of treatment. The treatment duration is sufficiently long to evaluate the safety and tolerability of safinamide 200 mg od and potentially show symptomatic efficacy. Approximately 56 participants will be screened to achieve 48 randomly assigned (2:1) to study intervention and 40 evaluable participants for an estimated total of respectively 26 and 14 evaluable participants per intervention group

The safety parameters will be assessed monitoring TEAEs and SAEs and changes (baseline – week 12) in physical and neurological examination findings, vital signs, 12-lead ECG and clinical chemistry and hematology values.

The efficacy parameters will be assessed looking at goniometric measurement for "lateral" and "anterior" displacement (Tinazzi, 2015) and assessing the changes (baseline – week 12) in the UMSARS (Wenning, 2004), the MSA-QoL (Schrag, 2007), the MoCA and the UDRS.

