9.3.2. Evaluable Population

The Evaluable Population will include all randomized participants. This population will be used for all efficacy variables.

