#### 2.2.3 Sample Size Determination

As this is a pilot study with a focus on evaluating the safety of safinamide, no formal sample size has been calculated. Approximately 56 participants will be screened to achieve 48 randomly assigned (2:1 active vs placebo) to study medication and 40 evaluable participants for an estimated total of respectively 26 and 14 evaluable participants per group.

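### Protocol 9.2 gives 26 vs 14 as the number enrolled although 48 are randomised 2:1, the 40 evaluable match no defined analysis set, and the size cannot resolve the 10-point AE excess it is meant to judge

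*Protocol*

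**What the plan says.** Protocol 9.2 states that "As this is a pilot study, no formal sample size has been calculated". It then states: "The current study enrolls 26 active vs 14 placebo". The next paragraph gives a different account: the plan is "to achieve 48 randomly assigned to study intervention and 40 evaluable participants". Only there does the pair 26 and 14 appear as a breakdown of the 40, given as "for an estimated total of respectively 26 and 14 evaluable participants per intervention group". That sentence also attaches the figure of about 56 participants to the phrase "randomized at a 2:1 ratio active: placebo", whereas Protocol 4.1 makes 56 the number screened: "Approximately 56 participants will be screened to achieve 48 randomly assigned (2:1) to study intervention and 40 evaluable participants". Protocol 1.1 agrees with 4.1.

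The population definitions use the same words differently. Protocol 9.3.1 counts as enrolled everyone who signs the consent form. Protocol 9.3.2 says "The Evaluable Population will include all randomized participants" and uses that set for all efficacy variables. SAP section 5 renames it the ITT Population, and SAP 3.2.2 defines ITT as everyone randomised. SAP 2.2.3 nevertheless keeps the older term: "Approximately 56 participants will be screened to achieve 48 randomly assigned (2:1 active vs placebo) to study medication and 40 evaluable participants", split 26 and 14. SAP 3.2 defines Screened, ITT, Safety and Per-Protocol populations, and none of them is called evaluable.

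On purpose, Protocol 9.4.1 and SAP 2.1 make safety and tolerability the primary objective. Protocol 9.3.3 and SAP 3.2.3 analyse safety in every randomised participant who takes at least one dose. Protocol 9.2 recalls AE rates in Parkinson's disease less than 10% above placebo. It judges the planned size sufficient to estimate whether AEs in MSA are likely to stay within that range.

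**The concern.** Within one section the same pair of numbers is the enrolment and the evaluable count. By the protocol's own definitions enrolled should mean about 56, randomised 48, and evaluable 48 again. A reader cannot tell from Protocol 9.2 how many patients per arm the sponsor had in mind when it called the size adequate. Nor can a reader tell which 8 of the 48 are expected to be lost, or by what criterion.

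The sample-size section is also the only place where the plan argues that the trial can meet its primary objective. That argument gives no precision, and its only per-arm counts are 26 and 14, which are not the counts in the set where safety is analysed. Once the right counts are used, the question is whether they can support a judgement about a 10-point excess.

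**Working it through.** **Inputs.** From Protocol 9.2, 4.1 and SAP 2.2.3: about 56 screened, 48 randomised, 2:1 allocation, 40 evaluable, 26 and 14 by arm. From Protocol 9.2: the 10% excess over placebo, read here as 10 percentage points. From Protocol 2.2: 81% and 74% of patients with adverse events in the earlier rasagiline trial in MSA. The 50%/50% and 20%/10% rates are assumptions, added to show a range. No alpha, power, effect size or dropout rate is stated.

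**Step 1: reproduce the plan's figures.** There is no power calculation to reproduce, only a chain of counts.
- 40 evaluable at 2:1: 40 × 2/3 = 26.7 and 40 × 1/3 = 13.3. The stated 26 and 14 are within one participant, so they fit as estimated evaluable counts.
- Implied loss from 48 to 40: 8/48 = 16.7%. Conversely, 40/(1 − 0.167) = 48. The chain closes.

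**Step 2: test the same figures as enrolment.**
- 48 at 2:1: 48 × 2/3 = 32 and 48 × 1/3 = 16. This split is derived; neither document prints it.
- 26 + 14 = 40, which is 8 short of 48 (6 short on active, 2 short on placebo).
- Under Protocol 9.3.1 enrolled would be about 56, 16 more than 40.

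**Step 3: test the word evaluable.** Under Protocol 9.3.2 the set holds all 48, not 40. Under the SAP the 48 are the ITT set, and the 40 belong to no named set.

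**Step 4: precision where safety is analysed.** For AE proportions p1 (active, n1) and p0 (placebo, n0), the normal-approximation half-width of the 95% interval for the difference is

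1.96 × √[p1(1 − p1)/n1 + p0(1 − p0)/n0].

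At 32 and 16, the most the Safety Population can be expected to hold:
- 50%/50%: 1.96 × √(0.25/32 + 0.25/16) = 0.300
- 81%/74%: 1.96 × √(0.1539/32 + 0.1924/16) = 0.254
- 20%/10%: 1.96 × √(0.16/32 + 0.09/16) = 0.202

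| AE rates, active/placebo | Half-width at 32/16 | Half-width at 26/14 | 32/16 half-width ÷ 10 points |
|---|---|---|---|
| 50% / 50% (assumed) | 30.0 points | 32.5 points | 3.0 |
| 81% / 74% (Protocol 2.2) | 25.4 points | 27.5 points | 2.5 |
| 20% / 10% (assumed) | 20.2 points | 22.0 points | 2.0 |

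As an illustration, if the trial observed exactly 81% and 74%, the difference of 7 points would carry an interval of 7 ± 25.4, from about −18 to +32 points. That is compatible both with no excess and with an excess three times the range in question.

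**The case against.** The fair defence has three parts.

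First, the text largely resolves itself. The second paragraph of Protocol 9.2 sets out 48 randomised and 40 evaluable, and Protocol 1.1, 4.1 and SAP 2.2.3 say the same. The administrative letter carries the same enrolment sentence beside a trial of about 40 subjects, so it reads as loose wording. The SAP's renaming leaves no analysis set called evaluable. This stands as far as it goes: the analyses can be run without ambiguity. It does not make the enrolment sentence true, and it does not say what the 40 are.

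Second, mislabelling costs little precision. Moving from 26/14 to 32/16 narrows the half-width by only about 2 points (2.5 at 50%, 2.1 at 81%/74%, 1.8 at 20%/10%). This stands. The imprecision comes from the size of the trial and remains after the labels are corrected.

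Third, this is a pilot with no formal size calculation, and Protocol 9.1 tests no safety hypothesis, so no power figure is affected. This also stands. But Protocol 9.2 goes further than calling the trial a pilot: it asserts sufficiency for a specific 10-point range, and that assertion can be checked.

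A reader might infer more than the documents support:
- **That 26/14 is a miscalculated split of 40.** It lies within one participant of 26.7/13.3, is labelled an estimate, and was confirmed by the sponsor in the administrative letter.
- **That the plan assumes different retention by arm.** Taking 26/32 = 81% and 14/16 = 88% at face value reads meaning into one participant of rounding. Moving that one participant to give 27 and 13 would yield 84% and 81% and reverse the direction.
- **That the 40 are Week 12 completers.** This is plausible, but no passage says so.

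**Conclusion.** The point holds as a fault of labelling and definition, together with an unsupported claim of sufficiency. The enrolment sentence in Protocol 9.2 is wrong on the section's own figures by 8 participants. The 40 evaluable correspond to no population in the protocol or the SAP, and the 16.7% loss behind them is unexplained. The sequence from 56 to 48 to 40 is arithmetically sound.

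The part with consequences is the precision. In the set that will actually be used for the primary objective, the AE-rate difference would be known only to within about 20 to 30 points, two to three times the excess the section says can be judged. This rests on a 32/16 split with everyone dosed, on a normal-approximation interval that is rough at these sizes, and on AE rates within the range shown. Fewer dosed participants in either arm would widen the interval at the same rates. The trial can describe AEs in MSA patients and would show a very large excess. It cannot be expected to separate an excess below 10 points from one well above it.

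**What to change.** In Protocol 9.2:
- Delete the sentence giving 26 and 14 as the enrolment.
- Attach the figure of about 56 to screening, in line with Protocol 1.1 and 4.1.
- Limit the sufficiency claim to what the precision supports: initial description of AEs and detection of large excesses.

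In Protocol 9.2 and SAP 2.2.3:
- State about 56 screened and 48 randomised (about 32 active and 16 placebo), all in ITT and, if dosed, in the Safety Population.
- Keep 40 (26 and 14) as an estimate. The sponsor should say what makes a participant count towards it, use a term distinct from the ITT set, and give the assumed 16.7% loss and its reason.
- State the expected 95% half-width for the AE-rate difference at 32/16 over a range of rates, for example the three in the table.

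The cost is wording only: no participants, visits or analyses are added. The drawback is that the stated ability to judge a 10-point AE excess becomes less favourable.

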9.3.3. Safety Population

The Safety Population will include all randomized participants who take at least one dose of study intervention. This population will be used to summarize all safety data; participants will be analyzed according to the intervention they actually received.

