9.4. Statistical Analyses

All statistical summaries will be descriptive in nature. All results will be presented separately for each of the study intervention groups. All analyses, summaries and listings will be performed using SAS version 9.4 or later.

All continuous variables will be summarized by presenting the number of participants, mean, standard deviation (SD), median, minimum and maximum. Categorical variables will be presented as frequencies and percentages.

A separate Statistical Analysis Plan (SAP) will be prepared to provide additional details on the definitions of the safety and efficacy variables, analysis approach, statistical justification

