9.4.1. Safety Analyses

The primary objective of this study is to evaluate the safety and tolerability of safinamide, 200 mg od, compared with placebo.

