9.4.1.1. Adverse events

Adverse events (AEs) will be coded using the Medical Dictionary for Regulatory Activities (MedDRA).

Adverse events will be classified as Treatment Emergent Adverse Events (TEAEs) or pretreatment AEs. An AE with an unknown/unreported onset date will also be counted as a TEAE.

An overview of adverse events categories will be summarized with counts and percentages. Categories will include:

- TEAEs
- Relationship to study intervention (possibly, unrelated)
- Action taken with study intervention (categories)
- Outcome (categories)
- Maximum severity of TEAE (mild, moderate, severe)
- Serious TEAEs

Treatment Emergent Adverse Events will also be summarized by System Organ Class (SOC) and Preferred Term (PT) within SOC with counts and percentages within each treatment group. Similar summaries will also be provided for Serious TEAEs and TEAEs related to study intervention.

A participant experiencing the same AE multiple times will be counted only once for the corresponding PT. Similarly, if a participant experiences multiple AEs within the same SOC, the participant will be counted only once for that SOC.

Analysis listings of serious TEAEs and study intervention-related TEAEs will be provided by study intervention group. The analysis listings will include a treatment-emergent flag, reported term, SOC, PT, start date, stop date, severity, relationship to study intervention, action taken with study intervention, outcome and seriousness.

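### Protocol 9.2 calls the sample size sufficient to judge an AE excess of under 10%, but gives no precision; the 95% interval for the difference would be roughly ±20 to 27 points, and none is planned

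*Protocol*

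**What the plan says.** Protocol 9.2 begins: "As this is a pilot study, no formal sample size has been calculated". It then cites Parkinson's disease studies as showing "Adverse Event rates in treated groups to be less than 10% in excess of placebo", and says that 48 randomised 2:1, giving 40 evaluable (26 and 14), was "judged to be sufficient to provide an estimate as to whether AEs are likely to be within this range in the MSA patient population". This is the only quantitative reason given for the size. The rasagiline trial is mentioned in the same section only to explain why a larger study was not chosen. SAP 2.2.3 repeats the numbers but not the 10% rationale.

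Protocol 9.4.1 states: "The primary objective of this study is to evaluate the safety and tolerability of safinamide, 200 mg od, compared with placebo". Protocol 9.1 says: "Safety data will be presented descriptively, thus no formal hypothesis for safety will be tested". Protocol 9.4 adds: "All statistical summaries will be descriptive in nature". For the analysis set, Protocol 9.3.3 says: "The Safety Population will include all randomized participants who take at least one dose of study intervention". TEAEs are to be summarised "with counts and percentages within each treatment group" (Protocol 9.4.1.1), and SAP 3.1.4 and 3.5.1 plan the same. Neither document plans a between-arm difference or interval for any AE measure. The 95% intervals that the SAP does specify are for the efficacy contrasts (SAP 3.4.1).

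**The concern.** The sentence in 9.2 concerns a difference between arms and a specific threshold. Saying that a sample size is enough to estimate whether an excess lies below 10% implies that the estimate will be precise on that scale. The protocol does not show this, and arms of about 32 and 16 make it doubtful.

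The stake is how the primary objective is read. A reader told that the size suffices may subtract the two percentages in the AE table, take a result under 10 points as reassurance or one over 10 as a signal, and see nothing that shows how far chance could have moved it.

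**Working it through.** **Inputs from the documents**
- Randomised: 48 at 2:1, so 48 × 2/3 = 32 safinamide and 16 placebo. These are the largest Safety Population arms the plan allows.
- Evaluable: 26 and 14, as stated. An exact 2:1 split of 40 would be 26.7 and 13.3, so the stated split is consistent.
- MSA rates from the rasagiline trial (Protocol 2.2): any AE 81% vs 74%, SAEs 35% vs 26%.

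The protocol has no sample size formula or precision figure to reproduce.

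**Assumptions**
- The 10% is an absolute difference.
- AE rates run from 10% to 74%. The upper end is the rasagiline-trial placebo rate. The lower end is my choice; the nearest document figure is the approximately 10% with severe TEAEs in Protocol 2.3.
- The interval is 95%, the level the SAP uses for its efficacy contrasts.

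**Step 1. Expected half-width.** With Wilson limits (l, u) in each arm and d = p1 − p0, the Newcombe interval runs from d − √[(p1 − l1)² + (u0 − p0)²] to d + √[(u1 − p1)² + (p0 − l0)²]. Half its width was averaged over all possible counts, weighted by their exact binomial probabilities. The Wald column is a cross-check: 1.96 × √[p(1 − p)(1/n1 + 1/n0)].

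| AE rate, both arms | Newcombe, 32 vs 16 | Wald, 32 vs 16 | Newcombe, 26 vs 14 |
|---|---|---|---|
| 10% | 20.1 | 18.0 | 22.0 |
| 20% | 23.3 | 24.0 | 25.2 |
| 50% | 26.9 | 30.0 | 28.7 |
| 74% | 24.6 | 26.3 | 26.5 |

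All entries are percentage points. At the rasagiline-trial rates with 32 vs 16, the half-width is 24.0 points for any AE and 25.2 for SAEs. True excesses of 0 to 20 points leave the 32 vs 16 range at 20.1 to 26.9.

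**Step 2. How often the interval spans 10 points.** Exact enumeration at 32 vs 16, placebo rates 10% to 74% in steps of one point:

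| True excess | Trials whose 95% interval contains 10 points |
|---|---|
| 0 | 80-90% |
| 7 points | 93-95% |
| 20 points | 85-91% |
| 30 points (placebo rates up to 70%) | 45-73% |

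**Step 3. What subtraction alone would show.** On the same grid, with no true excess the observed difference is 10 points or more in 11-24% of trials. With a true excess of 20 points it is below 10 in 20-27%.

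**Step 4. Two examples.**
- 27/32 vs 12/16 is 84.4% − 75.0% = +9.4 points. The Wilson limits are 68.2 to 93.1 and 50.5 to 89.8, so the interval is −12.5 to +35.4.
- 11/32 vs 4/16 is 34.4% − 25.0% = +9.4 points, interval −18.8 to +32.2.

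Both results look inside the range, and neither rules out an excess three times as large.

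**Step 5. Sensitivity.**
- A 5% AE rate still gives 17.9 points at 32 vs 16.
- An 80% interval gives about 12 to 18 points for rates of 10% to 74%.
- If 10% were relative, the threshold would be tighter: 0.10 × 74 = 7.4 points for any AE, or 0.10 × 26 = 2.6 points for SAEs, at the rasagiline-trial placebo rates.

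**The case against.** The best defence is that the sentence promises little. It follows a plain statement that this is a pilot with no formal calculation, offers only an estimate, and sets no margin, confidence level or decision rule. No endpoint or analysis uses the 10% figure. Safety is declared descriptive, and the administrative letter describes a pilot preceding an adequately powered efficacy study. The crude difference also falls on the correct side of 10 points in 76-89% of trials with no true excess and in 73-80% with a true excess of 20 points. Per-arm counts are a usual display for a pilot, and anyone can derive an interval from them.

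Much of this stands. No safety test is owed, and a power calculation is not missing. The 10% threshold comes from a Parkinson's disease trial whose AE measure and scale the protocol does not state, so the exact half-widths are illustrative. What does not stand is that pilot status supports a claim of sufficiency. It explains why nothing was calculated; it does not show that the size is adequate for the purpose named.

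Two stronger readings are tempting. A reader might infer that the sample size was miscalculated or the trial is underpowered for safety; the documents set no power or precision target, so there is nothing to fall short of. A reader might also infer that the interval would span 10 points in at least four trials out of five whatever the truth. Step 2 shows that this depends on the true excess: at 30 points the figure is 45-73%, so a large excess would often be distinguishable.

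**Conclusion.** The point holds as an unsupported adequacy statement. At the most favourable arm sizes, the uncertainty around the AE difference is about two to nearly three times the 10-point range it is meant to inform, and the planned tables show neither the difference nor its uncertainty, although the comparison with placebo is the primary objective. The half-widths rest on an absolute reading of 10%, assumed AE rates of 10-74%, a 95% Newcombe interval and 32 vs 16 dosed. Fewer evaluable patients, a relative reading, a 5% AE rate or an 80% level would not reverse the conclusion. No patient number and no planned analysis is wrong because of this; what needs correcting is one justification and one omission from the safety output.

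**What to change.** 1. In Protocol 9.2, replace the sufficiency statement with the expected precision and its assumptions. For example: *With at most 32 and 16 participants dosed, the 95% Newcombe interval for the absolute difference in AE rate is expected to have a half-width of about 20 to 27 percentage points, for assumed AE rates of 10% to 74%. The trial is not expected to confirm or exclude an excess below 10 points.* State also whether the cited 10% is absolute and which AE measure it describes.
2. In SAP 3.5.1, add the risk difference (safinamide minus placebo) with a 95% Newcombe interval in the Safety Population, labelled descriptive, at least for any TEAE and serious TEAEs.

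The cost is a few sentences, one small table and a less favourable justification for the size. No extra patients, visits or data are needed, and safety remains descriptive.
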